FSH	follicle-stimulating hormone
GCP	Good Clinical Practice
HIPAA	Health Insurance Portability and Accountability Act
HIV	human immunodeficiency
ICF	informed consent form
ICH	International Council on Harmonisation of Technical Requirements for Registration of Pharmaceuticals for Human Use
IRB	Institutional Review Board
IUD	intrauterine device
MedDRA	Medical Dictionary for Regulatory Activities
msec	millisecond(s)
PK	pharmacokinetic
QTcF	QT interval corrected for heart rate using the Fridericia formula
SAD	single ascending dose
SAE	serious adverse event
SAP	statistical analysis plan
SOC	system organ class
SpO ₂	Oxygen saturation
TEAE	treatment-emergent adverse event
T _{max}	time to reach maximum observed plasma drug concentration
UDS	urine drug screen
ULN	upper limit of normal

1. PROTOCOL SYNOPSIS AND SCHEDULE OF EVALUATIONS

CLINICAL STUDY SYNOPSIS: Study ITI-333-002	
Title of Study	A Randomized, Double-Blind, Placebo-Controlled, Multiple Ascending Dose Study to Evaluate the Safety, Tolerability and Pharmacokinetics of ITI-333 in Healthy Subjects
Study Center (Country)	1 (United States of America)
Development Phase	1
Objectives	
[REDACTED]:
 
 To determine the safety and tolerability of ITI-333 after multiple oral administration of ascending ITI-333 doses in healthy subjects To determine the pharmacokinetics of ITI-333 [REDACTED] after multiple oral administration of ascending ITI-333 doses in healthy subjects. 
[REDACTED]
 
[REDACTED]
 
[REDACTED]
 
[REDACTED]

Study Design	
This study will be conducted as a single-center, randomized, double-blind, placebo-controlled, dose escalation study of ITI-333 in up to 4 sequential cohorts.
 
Subjects will be screened up to 21 days prior to dosing with study drug. Subjects will be admitted to the study center on Day -1 and assessed for continued eligibility. On Day 1, subjects will be randomized to receive either ITI-333 or placebo. Dosing of study drug will occur after an overnight fast of at least 10 hours.
 
Each subject will receive an oral dose of study drug once daily for 14 days. Sentinel dosing will be used in each cohort. The first 2 subjects randomized in each cohort will receive either ITI-333 or placebo. Dosing of the remaining subjects within each cohort (5 subjects randomized to ITI-333; 1 subject randomized to placebo) will occur after a minimum of 24 hours from the Day 7 dosing of the sentinel group, to ensure adequate evaluation of safety and tolerability by the Investigator and Sponsor Study Physician.
 
Subjects in each cohort will be randomized to receive an oral dose of either ITI-333 or placebo once daily for 14 days. The planned doses are as follows:
 
 Cohort 1: 0.75 mg ITI-333 (n=6) or placebo (n=2) Cohort 2: 1.5 mg ITI-333 (n=6) or placebo (n=2) Cohort 3: 3 mg ITI-333 (n=6) or placebo (n=2) Cohort 4: 6 mg ITI-333 (n=6) or placebo (n=2) 
[REDACTED]
 
After completion of Cohorts 1 through 4, analyses of PK and safety data will be performed. Following the review of PK and safety data, stopping criteria may be modified.
 
Serial PK blood samples to determine plasma concentrations of ITI-333 [REDACTED] will be collected [REDACTED] on Day 14


	
(predose) and up to 72 hours after the last dose administration on Day 14. [REDACTED]
 
Following completion of all specified procedures, subjects will be discharged on Day 17. Subjects will return for a safety follow-up visit on Day 24 (± 1).
 
Upon completion of each cohort, a Data Monitoring Committee (DMC) will review safety and PK data to determine the progression of dose escalation. Dosing for the next higher dose cohort will not begin until the dose in the preceding cohort is deemed safe and tolerable and PK has been evaluated.

Number of Subjects	
A total of 32 healthy subjects (8 subjects per dose cohort) are planned for randomization. Within each cohort, 8 subjects will be randomized to receive multiple doses of ITI-333 (6 subjects) or placebo (2 subjects).

Main Criteria for Inclusion and Exclusion	
Inclusion Criteria:
 
 • Able to provide written, informed consent; • Healthy male or female subjects between 18 and 45 years of age, inclusive at time of consent; • Body mass index (BMI) between 18.0 and 32.0 kg/m², inclusive at Screening, and a minimum body weight of 50 kg at Screening. 
All Inclusion Criteria are presented in Section 6.3.1.
 
Exclusion Criteria:
 
 • Clinically significant abnormality within 2 years of Screening that in the Investigator's opinion may place the subject at risk or interfere with study outcome variables; this includes, but is not limited to, history of or current cardiac, hepatic, renal, neurologic, gastrointestinal, pulmonary, endocrinologic, hematologic, or immunologic disease or history of malignancy; • Any clinical condition or procedure (eg, gastric bypass or cholecystectomy) that may affect the absorption, distribution, biotransformation, or excretion of ITI-333. Subjects with a history of appendectomy are eligible for study participation; • Current or recent (within 3 months prior to Screening) unstable angina; a history of myocardial infarction within 3 months prior to Screening; or a history of a clinically significant cardiac arrhythmia; • History of psychiatric condition that in the Investigator's opinion may be detrimental to participation in the study; • Likely allergy or sensitivity to ITI-333 or its excipients based on known allergies or hypersensitivities to drugs with shared pharmacology which may be suggestive of an increased potential for an adverse reaction to ITI-333; • Received any medication including herbal medication, excluding non-hormonal IUD, within 5 half-lives or 14 days (whichever is longer) prior to dosing with study drug on Day 1; occasional use of acetaminophen (≤ 1 g/day) or ibuprofen (≤ 400 mg/day) during this period may be allowed on a case-by-case basis upon approval by the Sponsor; • [REDACTED] • Consumption of any food or beverage containing grapefruit, pomelo, poppy seeds, or Seville oranges within 48 hours prior to dosing with study drug on Day 1; • Females who are currently breastfeeding. 
All Exclusion Criteria are presented in Section 6.3.2.

Duration of Treatment	Study duration includes a Screening Period up to 21 days prior to dosing on Day 1, an inpatient Treatment Period of up to 17 days, and a Safety Follow-up Visit 10 days (\pm 1) day after the last dose of study drug. Therefore, the total study duration for each subject will be up to 46 days, including the Screening Period.
Test Product, Dosage, and Mode of Administration	
ITI-333 [REDACTED] will be supplied to the study center by the Sponsor [REDACTED]. [REDACTED] The planned ITI-333 doses in each cohort are:
 
 • Cohort 1: 0.75 mg ITI-333 once daily for 14 days • Cohort 2: 1.5 mg ITI-333 once daily for 14 days • Cohort 3: 3 mg ITI-333 once daily for 14 days • Cohort 4: 6 mg ITI-333 once daily for 14 days. 
Dose escalations other than the planned dosed specified above may be evaluated based on safety and PK assessments but they will not exceed 2-fold. [REDACTED]

Reference Product, Dosage, and Mode of Administration	Placebo [REDACTED], once daily for 14 days.
Pharmacokinetic Measures	
Blood samples to determine plasma concentrations of ITI-333 [REDACTED] will be collected at the following timepoints:
 
 • [REDACTED] • Day 14: predose, 0.5, 1, 1.5, 2, 3, 4, 6, 8, 12, 24, 48, and 72 hours postdose.
Safety Measures	
The safety and tolerability of ITI-333 will be assessed throughout the study via:
 
 • Adverse events (AEs) • Vital signs (blood pressure, [REDACTED] SpO₂, [REDACTED] weight, and body mass index [BMI]) • 12-lead electrocardiogram (ECG) • Clinical laboratory tests [REDACTED] • Prior and concomitant medications • Physical examination • [REDACTED] • Pregnancy test (where applicable)
[REDACTED]	[REDACTED]

[illegible]

• [REDACTED]
Plasma concentration data of ITI-333 [REDACTED]

[REDACTED] will be listed by subject using the Safety Population. For each analyte, plasma concentrations will be summarized using descriptive statistics by cohort, treatment day, and nominal sampling time using the PK Population. Descriptive statistics will be used to summarize PK parameters of ITI-333 [REDACTED] by cohort, using the PK population.

Safety Analysis:

2. ETHICAL CONSIDERATIONS

2.1 Institutional Review Board

Approval by the Institutional Review Board (IRB) before the start of the study will be the responsibility of the Investigator. A copy of the approval letter will be supplied to Intra-Cellular Therapies, Inc. (the Sponsor) or its designee along with a roster of IRB members. During the study, the Investigator will provide timely and accurate reports to the IRB on the progress of the study, at intervals not exceeding 1 year (or as appropriate) and will notify the IRB of serious adverse events (SAEs) or other significant safety findings. The study protocol, informed consent form (ICF), information sheet, advertisements, and amendments (if any) will be approved by the IRB at the study center in conformance with applicable regulations.

2.2 Ethical Conduct of the Study

This clinical study will be conducted in accordance with the ethical principles that have their origins in the Declaration of Helsinki. This clinical study will comply with the ICH Guidance on General Considerations for Clinical Trials (ICH-E8; 62 FR 66113, 17 Dec 1997) and GCP (ICH-E6; 62 FR 25692, March 2018), as well as CFR Part 312 and applicable local regulations.

2.3 Subject Information and Informed Consent

A written informed consent in compliance with US Title 21 Code of Federal Regulations (CFR) Part 50 shall be obtained from each subject before entering the study or performing any study-specific procedure that involves risk to the subject. If the ICF is revised during the study, all active participating subjects must sign the revised form. The informed consent statement shall contain all the elements of informed consent listed in [Appendix I](#) of this protocol.

Before any screening procedures, each prospective subject will be given a full explanation of the study and be allowed to read the approved ICF. After receiving an explanation of study procedures, subjects will have the opportunity to have any questions answered before signing the ICF. The Investigator must address all questions raised by the subject. Each subject will read, assent to an understanding of, and sign the ICF. Each subject will be made aware that he/she may withdraw from the study at any time.

The Investigator or designee will also sign the ICF and provide copies of the ICF and the HIPAA (Health Insurance Portability and Accountability Act) authorization or other locally applicable form to the subject. The Investigator shall retain the signed original ICF and the HIPAA or other locally applicable form.

3. STUDY ADMINISTRATIVE STRUCTURE

Contact information for vendors responsible for study conduct and a list of Sponsor contacts will be provided to the study center.

4. INTRODUCTION

ITI-333 uniquely combines high affinity binding to μ -opioid and serotonin 5-HT_{2A} receptors. In addition to the potential benefits conferred by ITI-333 affinity for μ -opioid receptors, the affinity of ITI-333 for 5-HT_{2A}, in concert with μ -opioid receptors, suggests a potentially unique functional pharmacological interaction that may have utility in the treatment of opioid use disorder (OUD) and the associated psychiatric comorbidities (eg, depression and anxiety).

Nonclinical data demonstrate that ITI-333 functions as a biased μ -opioid receptor ligand with partial agonist activity, acting as an antagonist to block effects of high doses of morphine in both pain and motor activity models while acting alone to provide potent analgesia in models of acute and chronic pain. However, when given to rodents at doses comparable to those that block the effect of morphine and well in excess of those required for analgesia, ITI-333 elicits no signs of physical dependence or tolerance after chronic dosing or after abrupt withdrawal of the compound.

In models designed to evaluate the safety pharmacology, ITI-333 did not induce biologically relevant effects on cardiovascular function in conscious cynomolgus monkeys and did not produce significant changes in respiratory rate, tidal volume, or minute volume in conscious rats. Evaluation of ITI-333 effects on gastrointestinal (GI) function showed that ITI-333 alone had no effect on GI propulsion in rats and yet ITI-333 blocked morphine-induced slowing of GI motility in rats. These data suggest that ITI-333 effectively mitigates some of the adverse symptoms associated with opioid use. ITI-333 lacks opioid-like abuse liability as it was not self-administered by rodents or non-human primates. Importantly, ITI-333 attenuates physical signs of naloxone-induced precipitated withdrawal in opioid dependent animals, indicating ITI-333 may alleviate symptoms of opioid withdrawal in humans.

[REDACTED]

[REDACTED]

[REDACTED]

[REDACTED]

[REDACTED]

[REDACTED]

Details on the profile of ITI-333 are provided in the current ITI-333 Investigator's Brochure.

5. STUDY OBJECTIVES

[REDACTED]

- To determine the safety and tolerability of ITI-333 after multiple oral administration of ascending ITI-333 doses in healthy subjects
- To determine the pharmacokinetics of ITI-333 [REDACTED] after multiple oral administration of ascending ITI-333 doses in healthy subjects.

[REDACTED]

- [REDACTED]
- [REDACTED]
- [REDACTED]

6. INVESTIGATIONAL PLAN

6.1 Overall Study Design and Plan

This study will be conducted as a single-center, randomized, double-blind, placebo-controlled, dose escalation study of ITI-333 in up to 4 sequential cohorts with 8 healthy male and female subjects to be randomized in each cohort, for a total of approximately 32 subjects. The study will be performed at 1 study center in the United States.

The study will be conducted as follows:

- A Screening Period of up to 21 days prior to dosing on Day 1
- A Treatment Period from Days 1-17
- A Safety Follow-up (SFU) Visit on Day 24 ± 1.

Following Screening, eligible subjects will be admitted to the study center on Day -1. On Day 1, subjects will be randomized to receive an oral dose of either ITI-333 (n=6) or placebo (n=2) once daily for 14 days. The planned doses in each cohort are as follows:

- Cohort 1: 0.75 mg ITI-333 (n=6) or placebo (n=2)
- Cohort 2: 1.5 mg ITI-333 (n=6) or placebo (n=2)
- Cohort 3: 3 mg ITI-333 (n=6) or placebo (n=2)
- Cohort 4: 6 mg ITI-333 (n=6) or placebo (n=2).

[REDACTED]

Sentinel dosing will be used in each cohort: the first 2 subjects in each cohort will receive either ITI-333 or placebo. Dosing of the remaining subjects within each cohort (5 subjects will receive ITI-333, 1 subject will receive placebo) will occur after a minimum of 24 hours from the Day 7 dosing of the sentinel group, to ensure adequate evaluation of safety and tolerability by the Investigator and Sponsor Study Physician.

A DMC will review safety and PK data to determine the progression of dose escalation before proceeding to the next cohort. Details related to the DMC and the review of the data will be provided in the DMC charter. Dosing for the next higher dose cohort will not begin until the dose in the preceding cohort is deemed safe and tolerable. Dose escalations other than the planned doses specified above may be evaluated based on safety and PK assessments but they will not exceed 2-fold.

[REDACTED]

[figure not shown]
[REDACTED]

[REDACTED]

[figure not shown]

6.2 Scientific Rationale for Study Design

6.2.1 Study Design

The design of this study is commonly used for the first-in-human multiple ascending dose evaluation of new investigational products. This study is designed as a randomized, double-blind and placebo-controlled study to avoid bias in the assessment of safety and tolerability of ITI-333. Subjects will receive an oral dose of study drug (either ITI-333 or placebo) once daily for 14 days.

Subjects will be dosed in sequential cohorts starting with the lowest dose. In addition, sentinel dosing will be used for each cohort. The first 2 subjects (1 active, 1 placebo) in each cohort will receive either ITI-333 or placebo. Dosing of the remaining subjects will occur after at least 24 hours post Day 7 dose of the sentinel group and after review of safety and tolerability data by the Investigator and Sponsor Study Physician. Subjects in the subsequent cohorts will be dosed after safety, tolerability, and PK have been evaluated in the previous cohort. Each cohort will include 6 subjects who will receive active study drug (ITI-333) and 2 subjects who will receive placebo.

6.3 Study Population

Subjects must meet all inclusion criteria and none of the exclusion criteria to be eligible to participate in the study. Subjects who do not meet the criteria for participation in the study may be re-screened upon approval by the Sponsor.

6.3.1 Inclusion Criteria

Subjects who meet all of the following criteria are eligible for enrollment:

1. Able to provide written, informed consent;
2. Healthy male or female subjects between 18 and 45 years of age, inclusive at time of consent;
3. Body mass index (BMI) between 18.0 and 32.0 kg/m², inclusive at Screening, and a minimum body weight of 50 kg at Screening;
4. Female subject:
 - a. Of nonchildbearing potential defined as either permanently sterilized (at least 4 months post-surgical sterilization which may include bilateral salpingectomy, tubal ligation or tubal occlusion, hysterectomy, or oophorectomy with or without hysterectomy) or postmenopausal (defined as amenorrhea for at least 12 consecutive months and documented follicle-stimulating hormone [FSH] level > 40 IU/mL; in the event a subject's menopausal status has been clearly established and yet FSH levels are not consistent with a postmenopausal status, determination of the subject's eligibility to be included in the study will be at the Investigator's discretion following consultation with the Sponsor); OR
 - b. Of childbearing potential and willing to practice one of the following highly effective methods of birth control: vasectomized partner or non-hormonal intrauterine device; OR willing to use 2 of the following methods: vaginal diaphragm with spermicide, condom with spermicide, or sponge with spermicide; OR remain abstinent from Screening through 90 days after the last dose of study drug; AND
 - c. Of childbearing potential or nonchildbearing potential with a negative serum pregnancy test at screening and a negative urine pregnancy test on Day -1;
5. Male subject who is permanently sterile (defined as bilateral orchidectomy or vasectomy, provided the absence of sperm has been medically confirmed) or if fertile (defined as post-puberty and not permanently sterile) must be willing to use a condom or remain abstinent AND abstain from sperm donation from Day -1 through 90 days after the last dose of study drug;
6. Willingness to follow protocol-defined restrictions;

7. Willing to be confined to the clinical research unit for the duration of the inpatient period of the study, and, in the opinion of the Investigator, willing and able to comply with all Investigator and staff instructions.

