8.1.2 Pregnancy

Female subjects will not be eligible for inclusion in the study if they have a positive pregnancy test at Screening or Day -1. Any subject who becomes pregnant must be discontinued from the study.

Study center staff must report every pregnancy, including pregnancies in female partners of male study subjects, from the time the ICF was signed until 90 days after the last dose of study drug.

Within 24 hours of learning of the pregnancy, study center staff must report the event to the Sponsor on the Pregnancy Notification and Outcome Form and email/fax it to the pregnancy email/fax number below even if no AE has occurred.

- While pregnancy itself is not considered to be an AE or SAE, any *pregnancy complication* or *elective termination* of a pregnancy for medical reasons will be reported as an AE or SAE. If the pregnancy is associated with an SAE (eg, spontaneous miscarriage or if the mother is hospitalized for hemorrhage), a separate SAE Report Form must be filed as described in [Section 8.1.1.5.2](#) with the appropriate serious criterion (eg, hospitalization) indicated on the SAE Report Form in addition to the Pregnancy Notification and Outcome Form.
- Abnormal pregnancy outcomes (eg, spontaneous abortion, fetal death, stillbirth, congenital anomalies, ectopic pregnancy) are considered SAEs and will be reported as such.

Any pregnancy in a study subject that has received at least one dose of study drug or in a female partner of a male study subject that has received at least one dose of study drug must be followed to term/termination. The outcome, including status of the mother and the child, must be reported to the Sponsor by completing a follow-up Pregnancy Notification and Outcome Form.

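### Inclusion 4b accepts a vasectomized partner as a woman's only contraception without the confirmation of sterility that Inclusion 5 requires, and leaves unclear which methods its 90-day window covers

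*Protocol*

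**What the plan says.** All the eligibility text on this point is in Protocol 6.3.1, and Inclusion 4 and 5 are fully legible.

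- **Inclusion 4a** (women of nonchildbearing potential) qualifies surgical sterilization by time: "at least 4 months post-surgical sterilization".
- **Inclusion 4b** (women of childbearing potential) offers three alternatives separated by semicolons. The first is one of the "highly effective methods of birth control: vasectomized partner or non-hormonal intrauterine device". The second is being "willing to use 2 of the following methods: vaginal diaphragm with spermicide, condom with spermicide, or sponge with spermicide". The third reads "OR remain abstinent from Screening through 90 days after the last dose of study drug".
- **Inclusion 4c** requires a negative serum pregnancy test at Screening and a negative urine test on Day -1.
- **Inclusion 5** (men) defines permanent sterility as "bilateral orchidectomy or vasectomy, provided the absence of sperm has been medically confirmed". A man outside that definition falls under the next clause: "if fertile (defined as post-puberty and not permanently sterile) must be willing to use a condom or remain abstinent". The criterion ends with a requirement to "abstain from sperm donation from Day -1 through 90 days after the last dose of study drug".

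Protocol 8.1.2 requires pregnancies to be reported "from the time the ICF was signed until 90 days after the last dose of study drug". It also requires a pregnant subject to be discontinued, and a pregnancy after any dose to be followed to its outcome.

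**The concern.** Two adjacent criteria judge the same procedure by different standards. Under Inclusion 5 a vasectomy without confirmed absence of sperm leaves a man in the fertile group, who must take further precautions. Under 4b the same vasectomy, in a partner, is enough as a woman's only method and carries the highly effective label. The standard that 4b lacks is the protocol's own.

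The second issue is the window. The closing phrase of 4b gives a start and an end, but it stands inside the abstinence alternative. A site reading the criterion as punctuated could conclude that a woman relying on her partner's vasectomy, an IUD or two barrier methods has made no commitment for any stated period.

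What is at stake is embryo-fetal exposure, or early pregnancy after exposure. Section 6.2.1 places the design among those used when multiple ascending doses are first given to humans, and Appendix I requires consent to mention unforeseeable risk to an embryo or fetus. Inclusion 4b is the entry criterion that guards against this.

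**Working it through.** There is no design figure to reproduce: the sample size rests on historical experience (Protocol 9.2), and no error rate or power is involved. The check is a comparison of text and a count of days.

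**Step 1. Vasectomy: the same man under two criteria.**

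| Situation | Criterion | Absence of sperm confirmed | Not confirmed |
|---|---|---|---|
| He is a subject | Inclusion 5 | Sterile | Fertile: condom or abstinence |
| He is a subject's partner | Inclusion 4b | Accepted as sole method | Accepted as sole method |

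The two criteria disagree only in the last column. Inclusion 4b asks neither for confirmation nor for a minimum time since the procedure. Inclusion 4a shows that the protocol does attach qualifiers to sterilization elsewhere. It does not show what qualifier would suit a partner.

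**Step 2. Is the condition supplied elsewhere?** The readable text of Section 7.6.2 (allowed concomitant medications, which include the non-hormonal IUD), Section 7.7 (diet, caffeine, alcohol, nicotine, activity) and Section 8.1.2 (pregnancy reporting) contains no vasectomy condition and no contraception duration. The SAP does not deal with eligibility.

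**Step 3. Scope of the window in 4b.** The three alternatives hold four routes: vasectomized partner, IUD, two barriers, abstinence.

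- Narrow reading: the semicolons close off the first two alternatives, so the window governs abstinence alone. Three of the four routes then have no stated start or end.
- Wide reading: the phrase closes the whole list, so all four routes run from Screening to 90 days after the last dose. This agrees with the reporting window in 8.1.2.

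The punctuation favours the narrow reading and the purpose favours the wide one. The text does not settle it.

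**Step 4. The period that depends on 4b.** Inputs: last dose Day 14, discharge Day 17, follow-up visit Day 24 ± 1 (Protocol synopsis and 6.1); 90 days (6.3.1 and 8.1.2).

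- End of window: 14 + 90 = Day 104.
- Days after discharge: 104 − 17 = 87 of the 90.
- Days after the last planned visit: 104 − 24 = 80 (79 to 81 with the visit window).

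Subjects are confined from Day -1 to Day 17, so all 14 dosing days are inpatient. Screening, of up to 21 days, is outpatient, but the tests at Screening and on Day -1 cover entry. The period left to the woman's commitment under 4b is therefore mainly the 87 days after discharge.

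**The case against.** The strongest reply is that the two criteria serve different ends. Inclusion 5 defines a participant's own fertility. Inclusion 4b concerns a partner who is not in the study and for whom the protocol describes no examination or access to records, so a question at Screening would yield the woman's report rather than medical confirmation. That is a fair point about how a condition could be met, and it bears on the cost of the change. It does not explain why the protocol spells out the condition for one man and omits it for the other.

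A reader might infer that sites would necessarily enrol a woman whose partner had a very recent vasectomy. The text permits this but does not compel it: Exclusion 32 lets the Investigator exclude anyone judged inappropriate. That is a general discretion, however, and does not replace a stated condition.

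A reader might also infer that the 90-day window plainly applies to abstinence alone, leaving three routes without a duration. The documents do not establish that. Inclusion 5 also ends in a trailing time phrase, and the same strict method would leave its condom requirement without a window too. What stands is an ambiguity that the semicolons make worse.

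Finally, it might be said that the risk is small, because dosing is inpatient and there are two entry pregnancy tests. This is correct for screening and dosing. It does not reach the period after discharge.

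**Conclusion.** The point holds as an inconsistency and an ambiguity in the eligibility text. Inclusion 4b, applied as written, admits a woman whose sole contraception is a partner whom Inclusion 5 would class as fertile, and no other readable section supplies the missing condition. The reach of the window in 4b across the other options is unclear.

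The exposed period is mainly Day 17 to Day 104, or 87 days, of which about 80 follow the last planned visit. This assumes 14 days of dosing and discharge on Day 17; Sections 7.1 and 8.2 allow the treatment and PK sampling periods to change, which would shift these days. The number of women affected cannot be estimated, because the documents do not give the sex mix or the methods used.

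Three stronger conclusions are not supported. The documents do not show that women in general enter on unproven contraception: the doubt concerns only an unconfirmed partner vasectomy, and an unclear end date does not make an IUD or two barrier methods unproven. The screening days should not be counted as equivalent risk, given the two tests. Discontinuation for pregnancy is a minor consequence for the trial, since most of the window lies after the final visit. The analyses, populations and dose-escalation data are not affected.

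**What to change.** Amend Inclusion 4b on two points.

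1. Reconcile its vasectomy condition with criterion 5, so that the two criteria no longer classify the same man differently. The sponsor should decide how, including what evidence a site can reasonably obtain about a partner.
2. State explicitly which of the listed options the Screening-to-90-days window covers, consistently with the 90-day reporting window in 8.1.2. The trailing phrase in Inclusion 5 could be checked in the same edit.

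The cost is one amended sentence and a check at Screening. If that check calls for more than the woman's own report, it will take more than one extra question. Some women may need another method already on the list. Nothing in the SAP has to change.
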